5.7 Interim Analyses

Safety and efficacy will be monitored on a regular basis by the Sponsor and the SAC. Possible adaptations resulting from these data reviews include:

- Modifying or stopping a cohort early based on a safety signal
- Expanding a cohort to include an additional approximately 15 participants (Stage 2) based on acceptable safety data in addition to preliminary signals in clinical activity and/or biomarker results

Other possible adaptations to the study design, including the addition of new combination cohorts, may be based on a variety of factors, such as emerging biological knowledge of mCRPC biomarkers and/or immunotherapy mechanisms, as well as availability of investigational therapies. Findings will not be used to re-estimate the sample size.

Due to the exploratory nature of this study, effect sizes and CIs will not be adjusted to account for ongoing review of data.

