3.3 Determination of Sample Size

The study is not intended or powered for hypothesis testing or comparison between cohorts. The study is intended to provide preliminary estimates of AE rates, response rates, effect sizes and CIs to aid the design of later studies. A sample size of approximately 15 participants per immunotherapy combination cohort will provide these preliminary estimates while limiting exposure.

Table 2 provides 95% exact confidence intervals for the proportion of participants experiencing a specific AE for sample sizes of 15 and 30 participants per cohort. These confidence intervals, along with the CRR (described below), provide information needed to assess the risk-benefit ratio of the immunotherapy combination for expanding the cohort to Stage 2 and for the design of further studies.

Table 2: Confidence Intervals for the True Proportion of Adverse Events

Observed AE rate	95% Confidence Interval (n = 15)	95% Confidence Interval (n = 30)
6.7% (1/15 or 2/30)	(0.2%, 31.9%)	(0.8%, 22.1%)
13.3% (2/15 or 4/30)	(1.7%, 40.5%)	(3.8%, 30.7%)
20.0% (3/15 or 6/30)	(4.3%, 48.1%)	(7.7%, 38.6%)
26.7% (4/15 or 8/30)	(7.8%, 55.1%)	(12.3%, 45.9%)
33.3% (5/15 or 10/30)	(11.8%, 61.6%)	(17.3%, 52.8%)
40.0% (6/15 or 12/30)	(16.3%, 67.7%)	(22.7%, 59.4%)

AE = adverse event

A Simon two-stage minimax design (Simon, 1989) will be implemented for each cohort. A CRR of at least 25% would provide sufficient evidence of clinical activity to warrant further investigation, while a CRR of 10% would not be of interest. In Stage 1, 15 participants will be enrolled. If the safety profile is acceptable and there are 2 or more responses in these 15 participants, 15 additional participants may be enrolled in Stage 2 for a total of 30 participants in the cohort. If there are 6 or more responses in these 30 participants, then the immunotherapy combination will be considered worthy of further investigation. This design yields a type I error rate of 0.07 and 77% power when the null hypothesis assumes the CRR is 10% and the alternative hypothesis assumes the CRR is 25%. Under the null hypothesis, the probability of terminating a cohort after Stage 1 is 55%.

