5.4.2.1 Composite Response Rate

CRR is a composite endpoint where response is defined as a participant meeting at least one of the following:

- CTC response: Change from unfavorable (≥ 5 cells/7.5 mL of blood) to favorable (≤ 4 cells/7.5 mL of blood). Participants with a missing baseline CTC value or baseline CTC value < 5 cells/7.5 mL of blood will not be evaluated for this criterion. The baseline CTC value is defined as the last available value recorded prior to the first administration of study intervention.
- PSA response: Confirmed PSA response is defined as $\geq 50\%$ reduction in PSA from baseline, with a repeat assessment confirming the result at least 3 weeks later. Participants without a PSA value at baseline will not be evaluable for this criterion. The baseline PSA value is defined as the last available value recorded prior to the first administration of study intervention.
- Objective radiographic response (ORR): Best overall response of CR or PR by objective radiographic disease assessment of soft-tissue, non-bone lesions, as determined by PCWG3-modified RECIST version 1.1. Per RECIST, to be assigned a best overall response of CR or PR, changes in tumor measurements must be confirmed by a repeat radiographic assessment performed no less than 4 weeks after the criteria for initial radiographic response were first met. In addition, responders must not have bone lesions that have progressed, as determined by PCWG3 criteria. Participants with measurable disease at baseline who received at least 1 dose of any component of the combination study intervention but do not have evaluable RECIST assessments for any reason will be counted as not responding. Participants without measurable, soft-tissue disease at baseline will not be evaluable for this criterion.

Response rates will be estimated within each cohort and 95% CIs will be estimated using the Clopper-Pearson method. Response rates and 95% CIs will also be presented for each individual criterion of CRR (CTC response, PSA response, and ORR).

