5.7.1 Cohort Expansion Rules

A Simon two-stage minimax design (Simon, 1989) will be implemented for each cohort. In Stage 1, 15 participants will be enrolled. If there are 2 or more responses in these 15 participants, 15 additional participants may be enrolled in Stage 2 for a total of 30 participants in the cohort. For the purposes of cohort expansion, CRR will be used to determine response (ie, CTC response, PSA response, or objective radiographic response).

In addition to efficacy criteria stated above, safety data will also be assessed when determining whether to expand a cohort. If there are ≥ 6 participants meeting cohort-specific toxicity criteria requiring permanent treatment discontinuation, an ad hoc SAC meeting will be held to further review all safety data and provide input on assessing the benefit-risk profile. The SAC will

provide a recommendation in regard to expansion to Stage 2, continuation or discontinuation of the cohort. This ad hoc review will be in addition to the ongoing safety monitoring performed by the SAC, who may recommend terminating a combination cohort at any time for safety reasons. The threshold of 6 participants was chosen because this translates to a posterior probability of 0.69 that the true toxicity rate is > 30%, assuming 15 participants are enrolled per cohort and a minimally informative beta (0.5, 2.5) prior.

If the cohort has an acceptable safety profile but has not demonstrated at least 2 responses, no additional participants will be enrolled into the cohort. However, this decision may be revisited if follow-up translational analysis or emerging external data identifies a subset of participants most likely to derive benefit from the combination therapy that was underrepresented in the cohort. Under this scenario, any modifications to the study design of the combination, including justification for participant selection or enrichment, will be detailed in an amendment to the appropriate cohort appendix.

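### CRR that triggers cohort expansion is later reported pooled and uncorrected, so it reads modestly high in expanded cohorts; report Stage 1 and Stage 2 rates beside it

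*SAP*

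**What the plan says.** SAP 5.7.1 ties cohort size to the endpoint that is later estimated: "If there are 2 or more responses in these 15 participants, 15 additional participants may be enrolled in Stage 2". The response counted there is the CRR, which the protocol calls ORR. SAP 3.3 adds the final rule: "If there are 6 or more responses in these 30 participants, then the immunotherapy combination will be considered worthy of further investigation".

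For estimation, SAP 5.4.2.1 says: "Response rates will be estimated within each cohort and 95% CIs will be estimated using the Clopper-Pearson method". SAP 5.7, citing the exploratory nature of the study, says that "effect sizes and CIs will not be adjusted to account for ongoing review of data", and Protocol 9.5 carries the same sentence. Neither document plans a two-stage estimator or separate rates by stage, and the list of departures in SAP 6 adds none. The SAP does not spell out that the estimate is responders divided by participants. That is inferred from the Clopper-Pearson method together with the no-adjustment sentence.

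On purpose, SAP 3.3 states: "The study is intended to provide preliminary estimates of AE rates, response rates, effect sizes and CIs to aid the design of later studies".

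**The concern.** An expanded cohort has been selected on its own early result, because its Stage 1 count cannot be 0 or 1. Pooling that half with an unselected Stage 2 half pulls the combined rate upward. The pull is strongest when the combination is weak, since weak combinations pass Stage 1 mainly by good luck. Cohorts that stop at 15 carry the opposite error.

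Expanded cohorts are the likelier source of planning figures for a later trial. A trial sized on an inflated rate would be somewhat underpowered. The sentence ruling out adjustment speaks of ongoing review, but as written it also covers the one planned, rule-based selection, whose effect can be calculated exactly.

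**Working it through.** **Inputs (SAP 3.3 and 5.7.1).** Stage 1 n = 15, continue at 2 or more responses; total n = 30, success at 6 or more; null CRR 10%, alternative 25%. The calculation treats the 2-of-15 rule as followed.

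**Reproducing the plan's figures.**
- Stopping under the null: 0.9^15 + 15 × 0.1 × 0.9^14 = 0.2059 + 0.3432 = 0.549. The SAP says 55%.
- Success: the sum over x = 2 to 15 of Bin(x; 15, p) × P(Bin(15, p) ≥ 6 − x) gives 0.0684 at p = 10% and 0.7745 at p = 25%. The SAP says: "This design yields a type I error rate of 0.07 and 77% power".

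The stated design is therefore reproduced.

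**Bias of the pooled rate.** Let X1 be the Stage 1 count.
- Mean Stage 1 rate given expansion = [15p − P(X1 = 1)] / [15 × P(X1 ≥ 2)].
- Stage 2 is not selected, so its mean is p. The pooled mean given expansion is the average of the two.
- Mean rate in stopped cohorts = P(X1 = 1) / [15 × P(X1 ≤ 1)].

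At p = 10%:
- Stage 1 given expansion: (1.5 − 0.3432) / (15 × 0.4510) = 17.1%.
- Pooled: (17.10 + 10) / 2 = 13.55%.
- Stopped cohorts: 0.3432 / (15 × 0.5490) = 4.17%.
- All cohorts: 0.4510 × 13.55 + 0.5490 × 4.17 = 8.40%.

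| True CRR | P(expand) | Stage 1 mean, expanded | Pooled mean, expanded | Bias, expanded (points) | Mean, all cohorts | Bias, all (points) |
|---|---|---|---|---|---|---|
| 10% | 45.1% | 17.10% | 13.55% | +3.55 | 8.40% | −1.60 |
| 15% | 68.1% | 19.75% | 17.38% | +2.38 | 13.38% | −1.62 |
| 20% | 83.3% | 22.96% | 21.48% | +1.48 | 18.77% | −1.23 |
| 25% | 92.0% | 26.69% | 25.85% | +0.85 | 24.22% | −0.78 |

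In responders out of 30, the excess in expanded cohorts is 0.0355 × 30 = 1.07 at 10% and 0.0085 × 30 = 0.26 at 25%.

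**Interval coverage (enumeration of every outcome).** Two-sided 95% Clopper-Pearson coverage over all cohorts is 99.2% at 10% and 96.3% at 25%, with a minimum of 95.0% for true rates from 2% to 60%. Among expanded cohorts it is 98.3% and 97.4%, and at least 95.7% for true rates of 10% or more. It drops below 95% only at some rates under 10%.

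**What each alternative buys.**
- *Stage 2 alone* is unbiased given expansion but less precise. Its root mean square error is √[p(1 − p)/15] = 7.7 points at 10% and 11.2 at 25%, against 5.9 and 7.5 for the pooled rate given expansion.
- *Stage 2 alone after success at 6 of 30* is selected again. At true 10% it averages 20.7%, against 21.7% pooled.
- *The two-stage UMVUE* has no bias over all cohorts, but in an expanded cohort it is the expected Stage 1 rate given the total, so its mean there equals the Stage 1 column: 17.1% at true 10% and 26.7% at true 25%. At 6/30 it gives 21.3% against 20.0% pooled.

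**The case against.** The best defence is that the choice is open and reasoned. Both documents say the study is exploratory, disclaim hypothesis testing and type I error control, and call the estimates preliminary. CRR is a secondary endpoint and safety is the only primary one. The bias is small beside the uncertainty: SAP Table 2 gives 7.7% to 38.6% for 6/30, about 31 points wide. The largest bias in the table arises at the null rate, where 55% of cohorts stop. The pooled rate also has smaller root mean square error than Stage 2 alone, so replacing it would make the planning figure noisier.

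All of this stands, and it sets the size of the point. It does not remove it. The exploratory label explains the lack of error control, but a study meant to supply estimates should at least disclose a bias of known direction.

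A reader might infer more than the documents support:
- *That type I error is inflated.* It is not. The Stage 1 look can stop only for too few responses, and the error is 0.0684 with the look against 0.0732 for a single-stage 6-of-30 rule.
- *That the confidence intervals are invalid.* Two-sided coverage is adequate across the 10–25% planning range.
- *That response rate is the trial's main object.* It is one of several quantities named, after adverse event rates.
- *That a UMVUE would cure the inflation.* In expanded cohorts it increases it.

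**Conclusion.** The point holds and is minor. It concerns the point estimate of CRR in expanded cohorts, not the decision rule or the interval. The pooled rate is too high on average by about 3.6 points at a true CRR of 10%, falling to 0.85 at 25%, and slightly too low over all cohorts.

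The figures assume that the 2-of-15 rule is followed and that each stage has exactly 15 participants. The documents allow some departure: sizes are approximate, the SAP says Stage 2 participants may be enrolled, safety and biomarker results also count, and a decision not to expand can be reopened. The Stage 2 rate stays unbiased given expansion under such discretion, provided Stage 2 enrols the same population. It would not if a cohort were reopened with the enrichment that SAP 5.7.1 permits. The UMVUE is exact only if the rule is binding.

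**What to change.** In SAP 5.4.2.1:
1. Keep the pooled rate with its Clopper-Pearson interval as the main estimate.
2. For each expanded cohort, also report the Stage 1 and Stage 2 rates separately, each with a Clopper-Pearson interval.
3. State that the pooled rate is biased upward given expansion, and that the Stage 2 rate is unbiased given expansion if both stages enrol the same population.
4. If a UMVUE is wanted, label it a supplementary overall estimate that assumes a binding rule, and say that it does not correct expanded cohorts.

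In SAP 5.7 and Protocol 9.5, limit the no-adjustment sentence to the informal ongoing reviews and refer to SAP 5.4.2.1 for CRR after the planned Stage 1 decision.

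The cost is two table rows per expanded cohort and a few lines of text, with no new data. The Stage 2 interval will be wide: by SAP Table 2, an observed 20% gives 4.3% to 48.1% at n = 15 against 7.7% to 38.6% at n = 30. Because the Stage 2 rate is also inflated among cohorts that pass 6 of 30, it should be read beside the pooled rate and not replace it.

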5.7.1 Cohort Expansion Rules

A Simon two-stage minimax design (Simon, 1989) will be implemented for each cohort. In Stage 1, 15 participants will be enrolled. If there are 2 or more responses in these 15 participants, 15 additional participants may be enrolled in Stage 2 for a total of 30 participants in the cohort. For the purposes of cohort expansion, CRR will be used to determine response (ie, CTC response, PSA response, or objective radiographic response).

In addition to efficacy criteria stated above, safety data will also be assessed when determining whether to expand a cohort. If there are ≥ 6 participants meeting cohort-specific toxicity criteria requiring permanent treatment discontinuation, an ad hoc SAC meeting will be held to further review all safety data and provide input on assessing the benefit-risk profile. The SAC will

provide a recommendation in regard to expansion to Stage 2, continuation or discontinuation of the cohort. This ad hoc review will be in addition to the ongoing safety monitoring performed by the SAC, who may recommend terminating a combination cohort at any time for safety reasons. The threshold of 6 participants was chosen because this translates to a posterior probability of 0.69 that the true toxicity rate is > 30%, assuming 15 participants are enrolled per cohort and a minimally informative beta (0.5, 2.5) prior.

If the cohort has an acceptable safety profile but has not demonstrated at least 2 responses, no additional participants will be enrolled into the cohort. However, this decision may be revisited if follow-up translational analysis or emerging external data identifies a subset of participants most likely to derive benefit from the combination therapy that was underrepresented in the cohort. Under this scenario, any modifications to the study design of the combination, including justification for participant selection or enrichment, will be detailed in an amendment to the appropriate cohort appendix.

6 DIFFERENCES COMPARED TO PROTOCOL

The following list provides a high-level overview of the differences between the SAP and the Core Protocol and cohort-specific appendices. The Core Protocol will be amended to address differences related to study endpoints.

- Section 3.2 (Study Objectives and Endpoints):
 - The SAP renames the Secondary composite endpoint from ORR to Composite Response Rate (CRR).
 - The SAP removes the requirement that at least 2 post-baseline PSA measurements must be available for a participant to be evaluable for the PSA response criterion of CRR.
 - The CRR criterion of confirmed response of CR or PR by objective radiographic disease assessment has been named ORR (objective response rate).
 - The SAP clarifies that participants without measurable disease at baseline will not be evaluable for ORR analysis.
 - The SAP modifies the minimum duration of SD required for a participant to be considered a DCR responder from 9 months to 6 months.
 - The SAP adds duration of response (DOR) as an exploratory endpoint.
- Section 3.3 (Determination of Sample Size): The SAP renames the Secondary composite endpoint from ORR to CRR.
- Section 5.1.1 (Evaluable Population): The SAP clarifies that some efficacy analyses may be performed on a subset of the evaluable population, as appropriate and detailed in other sections of the SAP.

- Section 5.4 (Efficacy Analysis): The SAP clarifies that some efficacy analyses may be performed on a subset of the evaluable population, as detailed in Table 3.
- Section 5.4.2.1 (Composite Response Rate):
 - The SAP renames the Secondary composite endpoint from ORR to Composite Response Rate (CRR).
 - The SAP clarifies that participants with a missing CTC value at baseline will not be evaluable for the CTC response criterion of CRR.
 - The SAP removes the requirement that at least 2 post-baseline PSA measurements must be available for a participant to be evaluable for the PSA response criterion of CRR.
 - The CRR criterion of confirmed response of CR or PR by objective radiographic disease assessment has been named ORR.
 - The SAP clarifies that participants without measurable disease at baseline will not be evaluable for ORR analysis.
 - The SAP clarifies that ORR responders must not have bone lesions that progressed, as determined by PCWG3 criteria.
 - The SAP clarifies that response rates and 95% CIs will be presented for each individual criterion of CRR.
- Section 5.4.2.2 (Disease Control Rate):
 - The SAP modifies the minimum duration of SD required for a participant to be considered a DCR responder from 9 months to 6 months.
 - The SAP clarifies that DCR responders must not have bone lesions that progressed, as determined by PCWG3 criteria.
- Section 5.4.3.2 (Circulating Tumor Cell Analysis): The SAP clarifies that participants with a missing CTC value at baseline will not be evaluable for the CTC0 analysis.
- Section 5.4.3.4 (Duration of Response): The SAP adds DOR as an exploratory endpoint.
- Section 5.7.1 (Cohort Expansion Rules): The SAP renames the Secondary composite endpoint used for expansion decision making from ORR to CRR.

8 APPENDICES

8.1 Core Protocol Synopsis (Protocol Amendment 2; 30 April 2019)

Protocol Title:

A Multicenter, Open-Label, Exploratory Platform Study to Evaluate Biomarkers and Immunotherapy Combinations for the Treatment of Patients with Metastatic Castration-resistant Prostate Cancer

Short Title:

Platform Study for Prostate Researching Translational Endpoints Correlated to Response to Inform Use of Novel Combinations (PORTER)

Rationale:

This study is designed to test multiple clinical hypotheses and mechanistically-defined combinations to evaluate the safety and efficacy of immunotherapy combination in participants with metastatic castration-resistant prostate cancer (mCRPC) who have received prior secondary androgen receptor signaling inhibitor therapy (eg, abiraterone, enzalutamide, apalutamide).

Key Objectives and Endpoints:

Objectives	Endpoints
Primary	
Incidence and severity of AEs.
Secondary	
ORR: A composite endpoint where response is defined as a participant meeting at least one of the following:
CTC response: Change from unfavorable (≥ 5 cells/7.5 mL of blood) to favorable (≤ 4 cells/7.5 mL of blood). Participants with a baseline CTC value < 5 cells/7.5 mL of blood will not be evaluated for this criterion.PSA response: Confirmed PSA response is defined as $\geq 50\%$ reduction in PSA from baseline, with a repeat assessment confirming the result at least 3 weeks later. Participants without a baseline and at least 2 post-baseline PSA assessments will not be evaluated for this criterion.Confirmed response of CR or PR by objective radiographic disease assessment using modified RECIST version 1.1 (ie, CR or PR and no progression in bone per the PCWG3; Scher et

	
al., 2016). Per RECIST, to be assigned a best overall response of CR or PR, changes in tumor measurements must be confirmed by repeat assessments that should be performed no less than 4 weeks after the criteria for response are first met. Participants who received at least 1 dose of the combination study intervention or component of the combination but do not have RECIST assessment for any reason will be counted as not responding.
 
• DCR at 9 months: Defined as CR, PR, or SD for 9 months as best response by PCWG3-modified RECIST 1.1. Participants who received at least 1 dose of the study intervention combination or component of the combination but do not have RECIST assessment for any reason will be counted as not responding.• rPFS: Defined as time from initiation of study intervention to the first objective evidence of radiographic progression, or death due to any cause (whichever occurs first).• OS: Defined as the time from initiation of study invention until death due to any cause.• OS rate at 12 months.
--	---

AE(s) = adverse event(s); CR = complete response; CTC = circulating tumor cells; DCR = disease control rate; ECOG = Eastern Cooperative Oncology Group; mCRPC = metastatic castration-resistant prostate cancer; ORR = objective response rate; OS = overall survival; PCWG3 = Prostate Cancer Clinical Trials Working Group 3; PR = partial response; PSA = prostate-specific antigen; RECIST = Response Evaluation Criteria in Solid Tumors; rPFS = radiographic progression-free survival; SD = stable disease

Overall Design:

This is an open-label, non-randomized, exploratory platform protocol designed to assess the safety and antitumor activity of multiple immunotherapy combinations in participants with mCRPC who have received prior therapy. The platform study will consist of 2 stages: Stage 1, an initial stage to evaluate safety, biomarkers, and clinical activity of a combination and Stage 2, an expanded cohort, when warranted, based on the safety, clinical activity, and/or biomarker results from Stage 1. The Sponsor intends to modify and/or add new combinations to the protocol as data emerge from this and other trials.

Participants must provide consent for archival tissue from a prior biopsy or surgery for prostate cancer and must consent to baseline and on-treatment biopsies, if medically feasible. Participants will be assigned to receive one of the enrolling combination study interventions and will be monitored for safety and response.

The duration of immunotherapy combination study intervention will be dependent on the combination administered and will continue for the duration described in the cohort appendix

for each respective combination, unless the participant: is no longer clinically benefiting (NLCB; as evidenced by symptomatic or radiographic disease progression and/or clinical deterioration); experiences any toxicity meeting specified discontinuation criteria (as described in the cohort appendix for each respective combination) or unacceptable toxicity in the best clinical discretion of the treating physician (ie, Investigator discretion); reaches the maximum duration of study intervention; or withdraws consent. Participants will be followed for up to 2.5 years from the time of the initiation of study intervention (see Follow-up). Depending on the combination administered, participants who are clinically benefiting, as defined by the Investigator at the end of the study treatment period, may have post-study access to the immunotherapy combination received during the study after written agreement from the Medical Monitor.

Number of Participants:

The study is not intended or powered for hypothesis testing. The study is intended to provide preliminary estimates of adverse event (AE) rates, response rates, effect sizes, and confidence intervals (CIs) to aid the design of later studies. A sample size of approximately 15 participants per combination intervention will provide these preliminary estimates while limiting exposure. An additional approximately 15 participants will be enrolled in Stage 2, if the cohort is expanded.

Intervention Groups and Duration:

This is not a randomized study. Assignment to one of the immunotherapy combinations will be made by the Investigator using his/her best clinical discretion based on the participant's medical history and disease status and knowledge of the available immunotherapy combinations open for enrollment.

The dose and schedule selected will be described in the cohort appendix for each respective combination (eg, Appendix Cohort A, Appendix Cohort B, etc.). The duration of immunotherapy combination study intervention will be dependent on the combination administered. Depending on the combination administered, participants who are clinically benefiting as defined by the Investigator at the end of the study may have post-study access to the immunotherapy combination after agreement from the Medical Monitor.

Follow-up:

For up to 2.5 years from the initiation of study intervention, participants in the follow up phase will be contacted by telephone by the site personnel every 3 months to collect alternate anticancer therapy information and determine survival status.

Participants will be followed for up to 2.5 years from the time of the initiation of study intervention unless the consent is withdrawn. All participants will be followed for safety for at least 100 days after discontinuation of study intervention.

Depending on the combination administered, participants who are clinically benefiting, as defined by the Investigator at the end of the study treatment period, may have post-study access to the immunotherapy combination received during the study after agreement from the Medical Monitor.

A participant will be considered lost to follow-up if he repeatedly fails to return for scheduled visits and is unable to be contacted by the study site.

Data Monitoring Committee:

[figure not shown]
This study will use a Safety Assessment Committee (SAC) of genitourinary (GU) oncologists and immuno-oncologists, who will meet regularly with the Sponsor to monitor safety on an ongoing basis.

Certificate Of Completion

Envelope Id: 3668B6C0C6334113ABC7EEB06492845C
 Status: Completed
 Subject: Please DocuSign: PICI0033 SAP v1.0 2021-01-29.pdf
 Source Envelope:
 Document Pages: 26 Signatures: 2
 Certificate Pages: 5 Initials: 0
 AutoNav: Enabled
 Envelope Stamping: Disabled
 Time Zone: (UTC-08:00) Pacific Time (US & Canada)
 Envelope Originator:
 [name]
 [name]
 [name]
 [contact]
 IP Address: [name]

[figure not shown]
Record Tracking

Status: Original Holder: [name] Location: DocuSign
 29-Jan-2021 | 10:45 [contact]

Signer Events	Signature	Timestamp
